APPENDIX B: CLINICAL LABORATORY ANALYTES

Standard Safety Chemistry Panel

Alanine aminotransferase	Albumin
Alkaline phosphatase	Amylase
Aspartate aminotransferase	Bicarbonate
Bilirubin (total, direct, and indirect)	Blood urea nitrogen
Calcium	Chloride
Creatine kinase	Creatinine
Estimated glomerular filtration rate	Gamma-glutamyl transferase
Glucose	Inorganic phosphorus
Lactate dehydrogenase	Lipase
Potassium	Sodium
Total protein	Uric acid

Hematology

Hematocrit	Hemoglobin
Platelets	Red blood cell count
White blood cell count and differential [1]	

1. Manual microscopic review is performed only if white blood cell count and/or differential values are out of reference range.

Coagulation

International normalized ratio

Urinalysis

Bilirubin	Blood
Glucose	Ketones
Leukocyte esterase	Microscopy [1]
Nitrite	pH
Protein	Specific gravity
Urobilinogen	

1. Microscopy is performed only as needed based on positive dipstick test results.

Other tests

Urine pregnancy test (females of childbearing potential only)

APPENDIX C: APACHE II SCORE FORM

	Physiologic Variable	High Abnormal Range					Low Abnormal Range				
		+4	+3	+2	+1	0	+1	+2	+3	+4	
1	Temperature rectal (°C)	≥41	39-40.9		38.5-38.9	36.0-38.4	34-35.9	32-33.9	30-31.9	≤29.9	
2	Mean arterial pressure = (2 x diastolic + systolic)/3	≥160	130-159	110-129		70-109		50-69		≤49	
3	Heart rate (ventricular response)	≥180	140-179	110-139		70-109		55-69	40-54	≤39	
4	Respiratory rate (non-ventilated or ventilated)	≥50	35-49		25-34	12-24	10-11	6-9		<5	
5	Oxygenation A-aDO ₂ or PaO ₂ (mmHg)										
	a)FiO ₂ >0.5:record A-aDO ₂	≥500	350-499	200-349		<200					
	b)FiO ₂ <0.5:record only PaO ₂					>70	61-70		55-60	<55	
6	Arterial pH If no ABGs record serum HCO ₃ below	≥7.7	7.6-7.69		7.5-7.59	7.33-7.49		7.25-7.32	7.15-7.24	<7.15	
7	Serum sodium	≥180	160-179	155-159	150-154	130-139		120-129	111-119	≤110	
8	Serum potassium	≥7	6-6.9		5.5-5.9	3.5-5.4	3-3.4	2.5-2.9		<2.5	
9	Serum creatinine (mg/dL) Double point for acute renal failure	≥3.5	2-3.4	1.5-1.9		0.6-1.4		<0.6			
10	Hematocrit (%)	≥60		50-59.9	46-49.9	30-45.9		20-29.9		<20	
11	White blood count	≥40		20-39.9	15-19.9	3-14.9		1-2.9		<1	
12	Glasgow Coma Scale (see next page) (Score = 15 minus actual GCS)	15 minus the GCS =									
A	Total Acute Physiology Score (APS)	Sum of the 12 individual variable points =									
*	Serum HCO ₃ (venous-mmol/L) Not preferred, use if no ABGs	<52	41-51.9		32-40.9	22-31.9		18-21.9	15-17.9	<15	

Glasgow Coma Scale (Circle appropriate response)		B Age Points	C Chronic Health Points	Apache II Score (sum of A+B+C)
Eyes open 4 - spontaneously 3 - to verbal 2 - to painful stimuli 1 - no response Motor response 6 - to verbal command 5 - localizes to pain 4 - withdraws to pain 3 - decorticate 2 - decerebrate 1 - no response	Verbal - nonintubated 5 - oriented and conversant 4 - disoriented and talks 3 - inappropriate words 2 - incomprehensible sounds 1 - no response Verbal - intubated 5 - seems able to talk 3 - questionable ability to talk 1 - generally unresponsive	Age Points <44 0 45-54 2 55-64 3 65-74 5 >75 6 Age points =	If any of the 5 CHE categories below is answered with yes, give +5 points for non-operative or emergency postoperative patients or +2 points for elective postoperative patients. Liver - Cirrhosis with PHT or encephalopathy Cardiovascular - Class IV angina or at rest or with minimal self-care activities Pulmonary - Chronic hypoxemia or hypercapnia or polycythaemia of PHT >40 mmHg Kidney - Chronic peritoneal or haemodialysis Immune - Immune compromised host Chronic Health Points =	A APS points (from prior page) + B Age points + C Chronic Health points ----- = Total APACHE II

A-aDO₂ = alveolar-arterial oxygen difference; ABG = arterial blood gases; APACHE = Acute Physiology and Chronic Health Evaluation; APS = acute physiology score; CHE = chronic health evaluation; FiO₂ = fraction of inspired oxygen; GCS = Glasgow coma scale; HCO₃ = bicarbonate; IV = intravenous; PaO₂ = arterial partial pressure of oxygen; PHT = pulmonary hypertension.

Source: Knaus WA, Draper EA, Wagner DP, et al. APACHE II: a severity of disease classification system. Crit Care Med. 1985;13(10):818-29

MedDRA	Medical Dictionary for Regulatory Activities			
MITT	Modified Intent-to-Treat			
РК	Pharmacokinetic(s)			
РО	Oral(ly)			
PP	Per-Protocol			
QD	Once daily			
SAE	Serious adverse event			
SAP	Statistical analysis plan			
SOC	Standard of care			
spp.	Species			
T2MR	T2 magnetic resonance			
TEAE	Treatment-emergent adverse event			
ULN	Upper limit of normal			
WHO	World Health Organization			

1. **INTRODUCTION**

The purpose of this Statistical Analysis Plan (SAP) is to provide a description of the statistical methods to be implemented for the analysis of data from the study with protocol number APX001-201 (Version 3.0, June 3, 2019). The SAP will be finalized prior to database lock. Any deviations from the SAP after database lock will be documented in the final Clinical Study Report (CSR).

2. STUDY OVERVIEW

2.1. Study Objectives

2.1.1. Primary Objective

The primary objective of this study is to evaluate the efficacy and safety of APX001 for the treatment of adult non-neutropenic patients ≥ 18 years of age with candidemia that may include patients with suspected or confirmed resistance to standard of care (SOC) antifungal treatment.

2.1.2. Secondary Objectives

The secondary objectives of this study are to:

- Evaluate the time to first negative blood culture;
- Evaluate the percentage of patients with Mycological Outcomes at the End of Study Drug Treatment (EOST), End of Antifungal Treatment (EOT), and 2 and 4 weeks after EOT;
- Evaluate the percentage of patients with Treatment Success at EOT, and 2 and 4 weeks after EOT;
- Evaluate overall survival at Study Day 30;
- Evaluate safety parameters, including number of patients with Treatment-emergent adverse events (TEAEs); and
- Evaluate Pharmacokinetic(s) (PK) parameters of APX001.

2.2. Study Design

This is a multicenter, open-label, non-comparative, single-arm study to evaluate the efficacy and safety of APX001 for the first-line treatment for candidemia including suspected or confirmed antifungal-resistant candidemia in non-neutropenic patients ≥ 18 years of age. Suspicion of antifungal-resistant candidemia is sufficient and subsequent documented resistance is not required for enrollment. The Study Drug Treatment Period will be up to a maximum of 14 days (inclusive of the loading dose [Study Day 1]). After completion of 14 days study drug therapy, if further antifungal treatment is indicated to complete treatment of candidemia in accordance with standard practice guidelines, fluconazole (unless susceptibility results warrant alternative antifungal therapy) may commence for up to a further 7 days. There will be a Follow-up Period of 4 weeks (+4 days) after EOT/EOST. The total duration of participation in the study is up to approximately 7.5 weeks (inclusive of the Screening Period [≤ 96 hours prior to Baseline]).

Patients with a yeast identified in a blood culture or a positive rapid diagnostic method are eligible to be consented and screened for the study. Patients must have at least 1 positive blood test for *Candida* species (spp.) (or yeast suspected to be *Candida*) for a diagnosis of candidemia to be considered for enrollment into the study. Patients with a positive blood culture showing yeast suspected to be *Candida* must have identification of *Candida* spp. from positive blood culture confirmed prior to dosing. Screening and Baseline procedures and the start of APX001 study drug will be initiated within 96 hours from the time that the SOC blood sample for the *Candida* spp. positive culture or rapid diagnostic test was drawn.

Patients with >2 days (>48 hours) equivalent of prior systemic antifungal treatment at approved doses to treat the current episode of candidemia within 96 hours before first dose will be excluded. However, patients with *Candida* infections proven to be resistant to the specific antifungal administered may have received ≤ 5 days (≤ 120 hours) equivalent of that prior treatment (results of susceptibility testing are required prior to enrollment).

All patients (or the patient's legal authorized representative [LAR]) will sign an Informed Consent Form (ICF) before any protocol specified procedures that are not indicated by SOC may be conducted. Inclusion/exclusion criteria assessments, medical history, demographics, and Acute Physiology and Chronic Health Evaluation (APACHE) II score will be collected before dosing.

On Study Day 1 (or over the first 24 hours if started in the evening), a 1000 mg APX001 loading dose will be administered over 3 hours by intravenous (IV) infusion Twice daily (BID). On Study Days 2 and 3 of study drug, a 600 mg APX001 maintenance dose will be administered over 3 hours by IV infusion once daily (QD). On Study Day 4 and onward, the APX001 maintenance dose will be administered as either 600 mg APX001 IV infusion QD over 3 hours or 700 mg oral (PO) QD. Patients who have completed a minimum of 3 days of IV APX001, are clinically stable as determined by the Investigator, able to swallow tablets, and have no further growth of the infecting organism 48 hours following the most recent blood culture, may switch from IV to PO dosing on Study Day 4 and onward. Study drug will be administered for a maximum of 14 days. At the Investigator's discretion, patients requiring a longer duration of antifungal therapy will be switched to fluconazole (unless susceptibility results warrant alternative antifungal therapy), to adhere to the IDSA clinical practice guidelines for the treatment of Candidiasis.

Candida spp. bloodstream infection will be monitored by daily blood culture during Study Drug Treatment until 2 consecutive blood cultures are negative, and at EOST, EOT, and 2 and 4 weeks after EOT, or Early Termination. Simultaneously drawn blood samples will be collected for *Candida* testing by T2 magnetic resonance (T2MR) assay at Baseline, during Study Drug Treatment, and EOST, or Early Termination. Other cultures, histopathology, and imaging tests to assess the site(s) and extent of candidemia infection at other sites will be conducted as clinically indicated, and the results should be recorded in the electronic Case Report Form (eCRF). The management of intravascular catheters, intravascular devices, and, if applicable, any drains will be recorded, including any associated microbiology results.

Patients will be monitored for safety throughout the duration of the study. Safety assessments will include vital signs, clinical laboratory assessments (serum chemistry, hematology, coagulation, and urinalysis), physical examinations (including neurological assessment), prior and concomitant medication reporting, and adverse event reporting. A 12-lead electrocardiogram (ECG) will be performed at Baseline (pre-dose), EOST, EOT, and 4 weeks after EOT, or Early Termination. A dilated fundoscopic examination will be performed at Screening for all patients and EOST, EOT,

and 4 weeks after EOT, or Early Termination for those patients who had positive fundoscopic findings at Screening, or as clinically indicated. A urine pregnancy test (for females of childbearing potential only) will be performed at Screening and Baseline (pre-dose), every 30 days during treatment if required by local regulations, EOST, EOT, and 2 and 4 weeks after EOT, or Early Termination.

[figure not shown]
Plasma samples for PK (APX001 [prodrug] and APX001A [active moiety]) will be collected at Baseline (pre-dose), twice weekly during Study Drug Treatment, EOST, EOT, 2 weeks after EOT, or Early Termination. Serum samples for (1,3)- β -D-glucan levels will be collected at Baseline (pre-dose) and EOST, or Early Termination (if applicable).

Optionally, if body fluids are sampled as part of routine patient management (e.g., bronchoalveolar lavage, lumbar puncture, paracentesis, vitreal fluid collection, abscess drainage), within approximately 2 hours of blood sampling for PK, these samples may be stored for future analysis of APX001 and APX001A levels.

The evaluation of treatment outcome will be assessed at EOST, EOT, and 2 and 4 weeks after EOT, or Early Termination. The end of study will occur after the last visit of the last patient on the study.

A schematic representing the study's design is included below.

TARE PERFORMS \$8 REALTS CONFLICTO ELIGIDADA Y ÉCRISSIONERIS

BC = blood culture; BID = twice daily; EOST = End of Study Drug Treatment; EOT = End of Antifungal Treatment; IV = intravenous(ly); PO = oral(ly); QD = once daily.

Table 1 presents the schedule of procedures of the study.

Table 1: Schedule of Procedures

				Treatme	nt Period[b]		Follo	ow-up	
Procedure	Eligibility	Screening (≤96 Hours of Baseline) [a]	Baseline (Day 1 Pre-Dose)	Study Drug Treatment (≤14 Days)	End of Study Drug Treatment (EOST)[c]	End of Antifungal Treatment (EOT)[e,f]	Follow-up 2 Weeks After EOT +2 Days	Follow-up 4 Weeks After EOT +4 Days	Early Termination
Informed consent		X[g]							
Inclusion/exclusion criteria		Х	X						
Medical history		Х							
Demographics		Х							
APACHE II score			Х						
Vital signs/temperature[h]		Х	х	Х	Х	Х	Х	Х	Х
Intravascular catheter/device management log (including any drains, if applicable)		X[i]	X[i]	Х	Х	X[j]	X[k]	X[k]	X
Dilated fundoscopic examination		Х			X[1]	X[d,l]		X[1]	X[1]
Clinical safety laboratory tests[m]		Х	X	Х	Х	X[d]	Х	Х	Х
12-lead electrocardiogram			Х		Х	X[d]		Х	Х
Urine pregnancy test (for females of childbearing potential only)		X	X	X[n]	Х	X[d]	X	X	Х
Physical examination[o]			Х	Х	Х	X[d]	Х	Х	Х
Blood sample for Candida spp. culture and testing by T2MR assay[r,s]	X	X[q]	X[p,q]	X[p,q]	X[p,q]	X[q]	X[q]	X[q]	X[p,q]

Table 1: Schedule of Procedures (Continued)

			Treatme	nt Period[b]	Follow-up				
Procedure	Eligibility	Screening (≤96 Hours of Baseline) [a]	Baseline (Day 1 Pre-Dose)	Study Drug Treatment (≤14 Days)	End of Study Drug Treatment (EOST)[c]	End of Antifungal Treatment (EOT)[e,f]	Follow-up 2 Weeks After EOT +2 Days	Follow-up 4 Weeks After EOT +4 Days	Early Termination
Blood samples for rapid									
diagnostic test[t]	Х								
Pharmacokinetic sample[u]			Х	Х	Х	Х	Х		Х
Other cultures and									
histopathology[k,v]		Х	X	Х	Х	Х	Х	Х	Х
Imaging tests[k,v]		Х	Х	Х	Х	X[d]	Х	Х	Х
Serum sample[w]			Х		Х				Х
Evaluation of treatment outcome					Х	Х	Х	Х	Х
Study drug administration[x]				Х					
Fluconazole treatment[y]						Х			
Prior/concomitant medications		Х	X	Х	Х	Х	Х	Х	Х
Adverse event									
evaluation		Х	X	Х	Х	Х	Х	Х	Х

a. To be completed within 96 hours from blood sampling time for culture positive for *Candida* spp.

b. During Study Drug Treatment, twice weekly visits are required with a maximum window of ±2 days. Outpatients will be asked to record daily dosing on a diary and bring the diary and study drug bottles with them to every clinic visit.

c. End of Study Drug Treatment (EOST) occurs after completion of APX001 dosing.

d. Assessments performed at EOST do not need to be repeated at End of Antifungal Treatment (EOT), if <48 hours apart, unless clinically indicated.

e. The EOST may be the same as EOT for those patients that do not have a step-down (i.e., fluconazole or other protocol approved step-down).

f. The EOT occurs up to a maximum of 21 days after Baseline (includes up to 14 days of APX001 administration and up to 7 days of fluconazole administration or other protocol approved step-down).

g. To be obtained prior to the initiation of any protocol-specific procedure outside of SOC.

h. Vital signs will include temperature, blood pressure, heart rate, respiratory rate, oxygen saturation, and weight. Vital signs will be collected at Screening, Baseline (pre-dose), daily on Study Days 2 to 4, and twice weekly thereafter during Study Drug Treatment, EOST, EOT, and 2 and 4 weeks after EOT, or Early Termination. Height will be collected (from the patient's medical record) at Baseline.

i. If possible, all indwelling intravascular catheters should be removed and the catheter tips cultured prior to starting APX001 dosing. The entrance site should also be cultured if it appears infected. Any removed catheter tip should be sent for culture.

j. Intravascular catheters logged until EOT.

- k. As clinically indicated. If obtained, results should be recorded in the eCRF.
- 1. Only required in those patients who had positive fundoscopic findings at Screening, or as clinically indicated.
- m. Screening laboratory assessments to determine eligibility will be performed at the local laboratory and may have been collected as SOC within the previous 24 hours. Laboratory assessments collected after Screening will be sent to the central laboratory for analysis. Clinical safety laboratory assessments (serum chemistry, hematology, coagulation, and urinalysis) will be collected at Baseline (pre-dose), twice weekly during Study Drug Treatment, at EOST, EOT, and 2 and 4 weeks after EOT, or Early Termination. If clinically indicated and at the discretion of the Investigator, or if a suspected adverse event is identified, clinical laboratory assessments may be conducted at any time during the study and compared to Baseline.
- n. Urine pregnancy test (for females of childbearing potential only) every 30 days if required by local regulations.
- A complete physical examination will be conducted at Baseline (pre-dose). Complete physical examination will include an assessment of general appearance, skin, eyes, heart, chest, abdomen, the body site that corresponds to the entry site of candidemia (e.g., central venous catheter entry site), if applicable, and a neurological examination. Components of the neurological examination include cranial nerve, sensory and motor examination, reflex and gait testing, and coordination assessment. A focused, symptom-based physical examination to include a neurological examination will be performed once weekly during study drug treatment, EOST, EOT, and 2 and 4 weeks after EOT, or Early Termination.
- p. Each time a blood culture is collected, an additional blood sample will be drawn for subsequent analysis of the correlation of blood culture and T2MR assay *Candida* spp. results from Baseline (pre-dose) through EOST or Early Termination. A central laboratory will perform the T2MR assay.
- q. Two consecutive sets of blood cultures during screening within 96 hours before the initiation of APX001 study treatment; 1 set thereafter.
- r. All Candida spp. isolates must be submitted to the mycology reference laboratory for confirmation of identification and susceptibility testing.
- s. During Study Drug Treatment, daily blood cultures on Study Days 1 through 4 (minimum), continuing until 2 consecutive blood cultures negative for *Candida* spp. are reported.
- t. Optional rapid diagnostic test, if available and used routinely for candidemia diagnosis; test (e.g., T2MR assay) must be Sponsor-approved; a subsequent confirmatory blood culture must also be performed to confirm *Candida* spp.
- u. Plasma samples for PK (APX001 [prodrug] and APX001A [active moiety]) will be collected at Baseline (pre-dose), twice weekly during Study Drug Treatment, EOST, EOT, 2 weeks after EOT, or Early Termination. Optional: If body fluids are sampled as part of routine patient management (e.g., bronchoalveolar lavage, lumbar puncture, paracentesis, vitreal fluid collection, abscess drainage), within approximately 2 hours of blood sampling for PK, these samples may be stored for future analysis of APX001 and APX001A levels.
- v. Other cultures, histopathology, and imaging tests to assess the site(s) and extent of candidemia infection, if applicable. If performed, these will be analyzed at the local study site.
- w. Serum samples for (1,3)-β-D-glucan levels will be collected at Baseline (pre-dose) and EOST, or Early Termination (if applicable).
- x. Study drug will be administered as an IV loading dose over 3 hours BID on Study Day 1 (or over the first 24 hours if started in the evening); on Study Days 2 and 3 study drug will be administered over 3 hours by IV QD; on Study Day 4 and onward, PO administration of the study drug may be considered if the patient meets the IV to PO switch criteria. Study drug will be administered for a maximum of 14 days (inclusive of the loading dose [Study Day 1]).
- y. After completion of 14 days study drug therapy, if further antifungal treatment is indicated to complete treatment of candidemia in accordance with standard practice guidelines, fluconazole (unless susceptibility results warrant alternative antifungal therapy) may commence for up to a further 7 days.

APACHE = Acute Physiology and Chronic Health Evaluation; BID = twice daily; eCRF = electronic Case Report Form; EOST = End of Study Drug Treatment; EOT = End of Antifungal Treatment; IV = intravenous(ly); PK = pharmacokinetic; PO = oral(ly); QD = once daily; SOC = standard of care; spp. = species; T2MR = T2 magnetic resonance.

3. SAMPLE SIZE DETERMINATION

A sample size of approximately 20 patients will be recruited in this open-label study. No formal statistical assessment for sample size determination has been performed. This sample size is considered adequate to provide the necessary data to evaluate the efficacy and safety of APX001.

4. INDEPENDENT DATA REVIEW COMMITTEE (DRC)

To ensure standardization of interpretation regarding the validity of study patients, the medical management, and response to treatment in this open-label study, a panel of recognized experts in the field of fungal infectious diseases will constitute a DRC. The DRC serves to provide independent oversight to confirm eligibility for efficacy analysis, to confirm the diagnosis of candidemia at study entry, and to adjudicate efficacy outcome. The DRC assessments for each patient will be recorded in the database and used in the primary efficacy analysis of the study. The DRC members will not be Principal Investigators in the study. Guidelines for the DRC are described in the DRC Charter.

5. DATA SAFETY MONITORING BOARD (DSMB)

A DSMB comprised of members with pertinent expertise will review the accumulating data from the study periodically as set forth in the DSMB Charter, or more frequently at the request of the DSMB. The DSMB will advise the Sponsor on the continuing safety of the study patients and those yet to be recruited to the study, as well as the continuing validity and scientific merit of the study. At any time, the independent DSMB may temporarily suspend enrollment until any significant safety concerns are resolved or terminate the study to ensure patient safety, if in the opinion of the DSMB, further dosing would pose an inappropriate safety risk. Guidelines for what constitutes inappropriate safety risks are described in the DSMB Charter.

6. STUDY ENDPOINTS

6.1. Primary Efficacy Endpoints

The primary efficacy parameter is Treatment Success at EOST as determined by the Data Review Committee (DRC).

6.2. Secondary Efficacy Endpoints

The secondary efficacy parameters include the following:

- Time to first negative blood culture;
- Percentage of patients with Mycological Outcomes at EOST, EOT, and 2 and 4 weeks after EOT;
- Percentage of patients with Treatment Success at EOT, and 2 and 4 weeks after EOT as determined by the DRC;

- Overall survival at Study Day 30; and
- Number of patients with TEAEs.

6.3. Exploratory Efficacy Endpoints

The exploratory efficacy parameters include the following:

- Change in serum (1,3)- β -D-glucan levels from Baseline (pre-dose) to EOST; and
- Correlation of blood culture and T2MR assay *Candida* spp. results from Baseline (pre-dose) through EOST.

6.4. Definitions for Efficacy Assessments

6.4.1. At End of Study Drug Treatment (EOST)

Treatment Success is defined as meeting all of the following criteria:

- Two consecutive blood cultures negative for *Candida* spp.;
- Alive at EOST; and
- No concomitant use of any other systemic antifungal therapies through EOST.

Treatment Failure is defined as any case that does not meet the criteria for Treatment Success.

Mycological Outcome:

• Eradication is defined as a negative blood culture(s) for *Candida* spp. in the absence of concomitant antifungal therapy through EOST.

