6.4.3 End of Study Drug Treatment

The EOST occurs after completion of APX001 dosing. The following procedures will be performed at EOST:

- Record vital signs, including temperature, blood pressure, heart rate, respiratory rate, oxygen saturation, and weight
- Intravascular catheter management log
- Perform dilated fundoscopic examination (only required in those patients who had positive fundoscopic findings at Screening, or as clinically indicated)
- Perform clinical laboratory assessments (serum chemistry, hematology, coagulation, and urinalysis)
- Perform 12-lead ECG
- Perform urine pregnancy test (for females of childbearing potential only)
- Perform focused, symptom-based physical examination including a neurological examination
- Collect blood culture for *Candida* spp. and blood for *Candida* spp. testing by T2MR assay
- Collect plasma sample for PK (APX001 [prodrug] and APX001A [active moiety])
 - Optional: If body fluids are sampled as part of routine patient management (e.g., bronchoalveolar lavage, lumbar puncture, paracentesis, vitreal fluid collection, abscess drainage), within approximately 2 hours of blood sampling for PK, these samples may be stored for future analysis of APX001 and APX001A levels.
- Collect other cultures and histopathology from other sites, as clinically indicated to monitor the site(s) and extent of candidemia infection
- Perform imaging tests as clinically indicated to monitor the site(s) and extent of candidemia infection
- Collect serum sample for analysis of (1,3)- β -D-glucan
- Evaluate treatment outcome
- Record concomitant medications
- Assess adverse events

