8.5.2 Subject Stopping Rule

Study treatment for an individual patient may be discontinued for lack of clinical and/or microbiological response, any adverse event, SAE, laboratory abnormality, or intercurrent illness which, in the opinion of the Investigator, indicates that continued dosing in the study is not in the best interest of the patient.

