7.4.2.5. DRC Assessments

Reasons for treatment failure according to DRC classifications (i.e. blood cultures did not become negative, or additional antifungals given, or died, or withdrew from study but did not die) will be summarized descriptively at EOST and EOT visits for the MITT and PP populations.

Reasons for relapse or other reasons for not having an outcome of sustained success at follow-up according to DRC classifications, will be summarized descriptively at 2 and 4 weeks after EOT for the MITT and PP populations.

Reasons for death according to DRC classifications (i.e. candidemia probably contributory, candidemia probably not contributory, or not known) will be tabulated for the MITT and PP populations.

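### A patient who clears, stops APX001 before Day 14, stays in the study and is then switched to another antifungal can count as Treatment Success on the primary endpoint, depending on visit timing and how the event is recorded

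*SAP*

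**What the plan says.** SAP 6.4.1 (matching Protocol 7.4.1 and the synopsis) sets three criteria for Treatment Success at EOST: "Two consecutive blood cultures negative for *Candida* spp", being alive at EOST, and "No concomitant use of any other systemic antifungal therapies through EOST". Failure is the remainder: "Treatment Failure is defined as any case that does not meet the criteria for Treatment Success".

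Protocol 6.4.3 fixes the time point only by reference to dosing: "The EOST occurs after completion of APX001 dosing". The schedule of procedures repeats this and allows up to 14 days of treatment. Neither place gives a minimum duration, a study day or an EOST visit window.

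Protocol 8.5.2 allows APX001 to be stopped without requiring the patient to leave the study: "Study treatment for an individual patient may be discontinued for lack of clinical and/or microbiological response, any adverse event, SAE, laboratory abnormality, or intercurrent illness". SAP 7.3.1 counts non-completion of 14 days of drug separately from non-completion of the study and links neither to outcome.

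SAP 7.4.2.5 lists the DRC's failure reasons at EOST and EOT: "blood cultures did not become negative, or additional antifungals given, or died, or withdrew from study but did not die". Stopping study drug early is not among them. Withdrawal from the study is, although it is not a criterion in 6.4.1.

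**The concern.** The primary rate is meant to describe APX001 as first-line treatment of candidemia. If EOST moves with the last dose, abandoning the drug also ends the period in which death or a replacement antifungal can count against it. A patient in whom APX001 was given up and replaced could then be credited to APX001. The trial is open-label with a single arm, so no comparator shares the bias, and the person deciding to stop knows the treatment.

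A second problem is reproducibility. Two patients with the same clinical course could be classified differently because one EOST visit fell a day later, or because one site recorded a drug discontinuation and another a study withdrawal.

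**Working it through.** The plan has no figure to reproduce: SAP section 3 gives about 20 patients with no formal calculation. The check applies the written criteria to defined cases and then sizes the effect.

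**1. Can success be reached early?** Cultures are daily on Study Days 1 to 4 (SAP 6.5.1), and Protocol 5.2.3 cites a median time to clearance of 2 to 3 days. Negative cultures on Days 2 and 3 meet the culture criterion after about 3 of 14 planned days.

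**2. Is replacement a likely consequence?** Protocol 5.2.3 cites guideline therapy lasting 14 days after documented clearance. A patient who stops on Day 4 is far short of that, so a further antifungal would be expected.

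**3. Apply the criteria.** In cases A to D the patient has negative cultures on Days 2 and 3 and stops APX001 on Day 4.

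| Case | What follows | Result on the text |
|---|---|---|
| A | Stays in study; EOST visit done; another antifungal starts next day | All three criteria met: Success |
| B | As A, but the antifungal starts before the EOST assessment | Antifungal criterion not met: Failure |
| C | Same event recorded as study withdrawal | Listed DRC failure reason (SAP 7.4.2.5), though not a criterion in 6.4.1 |
| D | EOST visit done; no replacement; dies on Day 6 | Alive at EOST: Success |
| E | Never two consecutive negatives | Culture criterion not met: Failure |

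A, B and C are the same clinical event. D shows that the survival criterion has the same gap. The carry-forward rule in SAP 7.1.2 moves an earlier failure to later visits; it never revises an EOST success.

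The missing window can also work against the drug. A patient who completes 14 days and starts step-down before the EOST visit would fail the antifungal criterion if it is read up to the visit.

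**4. Size per patient.** One patient of n moves the rate by 100/n points: 100/20 = 5.0 (100/18 = 5.6; 100/22 = 4.5).

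**5. Illustration.** The documents give no expected success rate, so 16 successes in 20 is an assumption. Exact (Clopper-Pearson) 95% intervals:

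| Successes reclassified | Rate | 95% CI |
|---|---|---|
| 0 | 16/20 = 80% | 56.3 to 94.3 |
| 1 | 15/20 = 75% | 50.9 to 91.3 |
| 2 | 14/20 = 70% | 45.7 to 88.1 |
| 3 | 13/20 = 65% | 40.8 to 84.6 |

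**6. Chance that early stopping arises at all.** With an assumed early-stopping rate p, P(at least one in 20) = 1 − (1 − p)^20. For p = 5%, 10%, 15% and 20% this gives 64%, 88%, 96% and 99%. These are upper limits for case A, which also requires clearance, a switch after EOST and staying in the study.

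**The case against.** Five points on the other side deserve weight.

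- **The DRC decides.** Its charter is not available and may cover this case. SAP 7.4.2.5 shows it may cite additional antifungals or withdrawal as failure reasons at EOST. A reader might infer that every switched patient is counted a success; the documents do not support that. What stands is that the published criteria permit it, and the SAP should not depend on an unseen charter.
- **The patient may be withdrawn.** Protocol 4.4 lists needing a prohibited medication, or a clinically significant adverse event, as grounds for ending participation. But that wording is permissive, and Protocol 5.6.2 bars other antifungals for candidemia only while the patient is receiving APX001.
- **Poor response is mostly caught.** Patients without two consecutive negatives already fail. Only clinical worsening or intolerance after culture clearance is affected.
- **Nothing is hidden.** Reasons for not completing 14 days, additional antifungals, exposure, adverse events leading to discontinuation, later outcomes and Day 30 survival are all reported, and there is no test or threshold to flip. This limits the harm but does not correct the headline rate.
- **An on-treatment endpoint is a legitimate choice**, with EOT as a separate assessment. That is fair, but it would still need a defined EOST for early stoppers and one rule for cases A to C. If completion of dosing is read as completing all 14 days, EOST is undefined for these patients, which also needs repair.

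**Conclusion.** The gap is real and concerns the primary endpoint. On the text, a cleared patient who stops APX001 before Day 14, remains in the study and is switched after EOST can be a Treatment Success, while the same event timed or recorded differently is a failure. The error in case A favours the drug.

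The only firm size is 5 points per such patient at n = 20. The 80% versus 65% comparison is arithmetic on assumed counts, not an estimate of bias.

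A reader might also infer that the EOT endpoint is certain to catch these patients, because step-down is described only after 14 days of study drug. Failure at EOT is likely but not certain: Protocol 6.4.4 ties EOT to completing 14 days, while the schedule footnotes refer to up to 14 days, so EOT is unclear for early stoppers. EOT is in any case secondary and does not correct the primary rate.

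The conclusion assumes that the DRC applies the SAP criteria as written.

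**What to change.** These changes concern outcome classification only, not how patients are treated.

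1. In SAP 6.4.1, Protocol 7.4.1 and the synopsis, anchor EOST to the last APX001 dose date and state a visit window. For patients who complete 14 days, assess other antifungals through the last dose date, so that step-down started before the visit does not count against them.
2. For patients who stop APX001 before Day 14, assess both survival and other systemic antifungals for candidemia through Study Day 14. Early stopping followed by replacement in that period is then a Treatment Failure, as is death by Day 14.
3. Add study drug stopped early and replaced to the failure reasons in SAP 7.4.2.5. Make the withdrawal reason agree with 6.4.1, and align the DRC Charter.
4. Report the present rule as a sensitivity analysis.

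The cost is wording in the SAP, protocol and charter and a line on the DRC form, settled before database lock. Concomitant antifungals (SAP 7.3.6) and reasons for not completing 14 days (SAP 7.3.1) are already collected. The sample size is unaffected, since it was not calculated. The downside is that the rate may be slightly less favourable, and a patient switched for tolerability or an unrelated event counts as a failure. The sensitivity analysis shows how much that matters.
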